2.0 TRIAL DESIGN

2.1 Trial Design

This is an open-label, single-dose, multiple panel trial to evaluate the safety, tolerability, pharmacokinetics (PK), and anti-retroviral therapy (ART) activity of MK-8583 monotherapy in ART-naïve, Human Immunodeficiency Virus type 1 (HIV-1) infected subjects. The primary study endpoints are the safety and tolerability of MK-8583 and the change in plasma HIV-1 RNA (log₁₀ copies/mL) compared with historical placebo data. This study will be conducted in conformance with Good Clinical Practices.

Up to three panels of 6 subjects each will be enrolled in a sequential manner. All doses of study drug will be administered following at least an 8-hour fast. In each panel, subjects will receive a single dose of MK-8583. Safety procedures and biological specimen collections will occur at designated time points. Subjects in Panel A will receive a single oral dose of MK-8583 100 mg. The exact dose administered in Panels B and C will be selected following review of all available safety, PK and viral dynamic data from prior panel(s); the dose will not exceed 150 mg. There will be an interval of time between dosing of panels to allow for

review of safety, PK, and viral dynamic data to inform dose selection in the following panel. It is estimated that this review will take approximately 30-40 days.

Initiation of ART: At a designated time following administration of study drug, subjects will be encouraged to initiate an ART regimen. The exact timing and regimen will be decided by the subject in consultation with his/her physician, but ART initiation will not occur before Day 10 post-dose (see Section 5.5). Once initiated, the duration of suppressive ART is recommended to be at least ~25 days, or approximately 5 half-lives of tenofovir diphosphate (TFV-DP) in peripheral blood mononuclear cells (PBMCs). To lessen the chance of HIV resistance mutations, the Sponsor recommends that ART initiation occurs on or before Day 14 post-dose. The Sponsor will not provide this therapy.

The initiation of follow-on ART is not a requirement for participation in the study. All subjects will be followed for safety monitoring for a maximum of approximately 28 days after dosing of MK-8583. If subjects start ART as planned, on Day 10 through 14 after dosing, the final blood draw for viral load (VL), viral resistance, or PK will occur on the day of ART initiation (prior to receiving the first dose of ART).

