5.5 Concomitant Medications/Vaccinations (Allowed & Prohibited)

If a subject does not discontinue all prior medications within 14 days or 5 half-lives of starting the trial, he/she may be included in the study if the investigator can rationalize that the specific use of a prior medication is not clinically relevant within the context of the trial.

Concurrent use of any prescription or non-prescription medication, or concurrent vaccination, during the course of the trial (i.e., after randomization or treatment allocation) must first be discussed between the investigator and Sponsor prior to administration, unless appropriate medical care necessitates that therapy or vaccination should begin before the investigator and Sponsor can consult. The subject will be allowed to continue in the trial if both the Sponsor and the investigator agree.

Paracetamol/acetaminophen may be used for minor ailments without prior consultation with the Sponsor.

Initiation of ART: All subjects will be encouraged to initiate ART some interval after their dose of MK-8583. The exact timing and regimen will be decided by the subject in consultation with his/her physician, but ART initiation will not occur before Day 10 (240 hours post-dose). This timing is required to gather full efficacy data for this novel long-acting anti-retroviral compound and is consistent with prior anti-retroviral monotherapy proof-of-concept trials, in which low-dose anti-retroviral monotherapy has been administered for as long as 28 days [10] and with European Medicines Agency (EMA) guidance [5]. If the physician and/or Investigator believe there is a strong indication to start ART before Day 10, this should be discussed with the Sponsor prior to starting, as with other concomitant medications (see above).

To lessen the chance of HIV resistance mutations developing, the Sponsor recommends that ART initiation occurs before PBMC TFV-DP concentrations fall below 100 nM. (100 nM is set as the lower limit because this is the steady-state Ctrough of TDF.) In Panel A (100 mg dose), the PBMC TFV-DP concentration is expected to fall below 0.1 μM after 4 half-lives, or ≥ 14 days, and therefore it is recommended that ART is initiated on or before Day 14. In subsequent panels, the Sponsor will provide the site with written guidance, prior to the start of dosing, as to the time when PBMC TFV-DP concentrations are expected to fall below the 100 nM lower limit.

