a.	The post-trial visit will occur approximately 28 days following administration of the study drug. Follow up for any clinical or laboratory adverse experiences should occur by phone or in person if the post-trial visit occurs prior to 28 days following the last dose of study drug. For confirmation of viral load return to baseline, additional data from viral load samples collected during routine follow-up visits may be transmitted to the sponsor for those patients who do not begin ART and who provide appropriate informed consent. Subjects may be asked to participate in observational monitoring beyond the 672 hour post-trial visit.																		
b.	This sample should be drawn for planned analysis of the association between genetic variants in DNA and drug response. This sample will not be collected at the site if there is either a local law or regulation prohibiting collection, or if the IRB/IEC does not approve the collection of the sample for these purposes. If the sample is collected, leftover extracted DNA will be stored for future biomedical research if the subject signs the FBR consent. If the planned genetic analysis is not approved, but FBR is approved and consent is given, this sample will be collected for the purpose of FBR. This sample, to be collected on randomized subjects only, should be obtained one time only, pre-dose, on Day 1.																		
c.	On Day 1, the randomization number is assigned after the completion of all pre-dose procedures prior to trial drug administration.																		
d.	The pre-dose PE, laboratory assessments, and urine/blood drug screen may be performed within 24 hours prior to dosing.																		
e.	Pre-dose ECGs will be obtained in triplicate, at least 1-2 minutes apart, and will be obtained within 3 hours prior to dosing of the trial drug. Pre-study and post-dose ECGs will be single measurements. Subjects should be resting in a semi-recumbent position for at least 10 minutes prior to obtaining ECG. See Section 7.1.2 for additional details.																		

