f.	Pre-dose semi-recumbent HR and BP will be triplicate measurements obtained at least 1-2 minutes apart within 3 hours prior to study administration. Subjects should be resting in the semi-recumbent position for at least 10 minutes prior to obtaining HR and BP. Following each semi-recumbent HR and BP measurement, subjects assume a standing position for at least ~2 minutes and then orthostatic HR and BP will be obtained. Pre-study and post-dose vital sign measurements will be single measurements. See Section 7.1.2 for additional details.																		
g.	Standardized meals will be provided at ~4 and ~10 hours post-dose. A snack will be offered at ~7 and 13 hours post-dose. After the 24 hour post-dose procedures have been completed, subsequent meal and snacks will be unrestricted in terms of caloric content, composition and timing.																		
h.	For female subjects of childbearing potential only. Urine pregnancy test may be performed instead of serum at pre-dose.																		
i.	For postmenopausal woman only.																		
j.	Additional urine drug screen tests may be performed at the discretion of the Investigator.																		
k.	Leftover main study plasma will be stored for future biomedical research, if the subject consents to Future Biomedical Research consent.																		
l.	For all panels, PBMC samples may be collected up to the post-trial visit regardless of initiation of ART.																		
m.	For all panels, blood for HIV-1 viral RNA (also called viral load, VL) and viral resistance may be collected up to and including the day of ART initiation. Subjects choosing to forgo follow-on ART may also be asked if they wish to continue to participate in observational monitoring of VL and viral resistance testing beyond 28 days.																		
n.	The 672 hour sample may be collected at the post-trial visit. Leftover main study PBMC will be stored for future biomedical research if the subject consents to Future Biomedical Research consent.																		
o.	Informed consent for future biomedical research samples must be obtained to collect the stool samples. Stool samples will be collected at any time before dosing, according to the instructions in the Study Operations Manual. But if a sample cannot be obtained prior to dosing, this subject will be omitted from stool collection, the dosing will still proceed as scheduled and this will not be considered a protocol deviation.																		

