7.2 Assessing and Recording Adverse Events

An adverse event is defined as any untoward medical occurrence in a patient or clinical investigation subject administered a pharmaceutical product and which does not necessarily have to have a causal relationship with this treatment. An adverse event can therefore be any unfavourable and unintended sign (including an abnormal laboratory finding, for example), symptom, or disease temporally associated with the use of a medicinal product or protocol-specified procedure, whether or not considered related to the medicinal product or protocol-specified procedure. Any worsening (i.e., any clinically significant adverse change in frequency and/or intensity) of a preexisting condition that is temporally associated with the use of the Sponsor's product, is also an adverse event.

Changes resulting from normal growth and development that do not vary significantly in frequency or severity from expected levels are not to be considered adverse events. Examples of this may include, but are not limited to, teething, typical crying in infants and children and onset of menses or menopause occurring at a physiologically appropriate time.

Sponsor's product includes any pharmaceutical product, biological product, device, diagnostic agent or protocol-specified procedure, whether investigational (including placebo or active comparator medication) or marketed, manufactured by, licensed by, provided by or distributed by the Sponsor for human use.

Adverse events may occur during clinical trials, or as prescribed in clinical practice, from overdose (whether accidental or intentional), from abuse and from withdrawal.

For randomized subjects only, all adverse events that occur after the consent form is signed but before treatment allocation/randomization must be reported by investigator if they are the result of a protocol-specified intervention, including but not limited to washout or discontinuation of usual therapy, diet, placebo treatment or a procedure. From the time of treatment allocation/randomization through 28 days following cessation of treatment, all adverse events must be reported by the investigator. Such events will be recorded at each examination on the Adverse Event case report forms/worksheets. The reporting timeframe for adverse events meeting any serious criteria is described in section 7.2.3.1. The investigator will make every attempt to follow all subjects with non-serious adverse events for outcome.

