8.2.4 Statistical Methods

Primary (Safety)

Incidence of adverse experiences will be descriptively summarized. Summary statistics and plots will be generated for the change from baseline values in the vital signs, ECG parameters, and selected laboratory safety parameters for subjects, as deemed clinically appropriate. Depending on the safety parameter, the difference from baseline will either be computed on the original scale (raw change from baseline) or on the log scale and back-transformed for reporting (percent change from baseline). Summary statistics for the raw laboratory safety tests, ECGs, and/or vital signs may also be computed, as deemed clinically appropriate.

Primary (Pharmacodynamics)

The log₁₀ plasma HIV-RNA (copies/mL) measurements from subjects in all panels will be pooled and analyzed based on a longitudinal data analysis (LDA) model containing fixed effects for dose level, time (pre-dose, 168 hrs post-dose) and dose level by time interaction, and a random effect for patient. The response vector consists of the baseline and 168 hours post-baseline values. Time is treated as a categorical variable so that no restriction is imposed on the trajectory of means over time. The change from baseline for each dose level at 168 hours post-baseline will be estimated from this model. A posterior distribution for the true mean change from baseline at 168 hours will be generated for each dose level using flat priors under a normal likelihood assumption. Historical placebo data from recent monotherapy studies in HIV-1 subjects (MK-0518 Protocol 004, MK-1439 Protocol 005, MK-6186 Protocol 007, and MK-1972 Protocol 003) will be separately analyzed based on a longitudinal data analysis model containing fixed effects for study and time (pre-dose, 168 hrs post-dose), and a random effect for patient. The change from baseline for placebo at 168 hours post-baseline will be estimated from this model, and a posterior distribution for the true

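### Does the safety analysis need a pre-specified split at the start of follow-on ART?

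*Combined protocol and SAP*

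**What the plan says.** Safety and tolerability is one of the two primary objectives (Section 3.1). The adverse-event method is a single sentence, given identically in 8.1 and 8.2.4: "Incidence of adverse experiences will be descriptively summarized". Laboratory, ECG and vital-sign changes from baseline get summary statistics and plots, with the choice left to clinical judgement. The safety population (ASaT, 8.2.3) is everyone dosed, with no censoring at a later event.

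Section 7.2 sets the collection window: "From the time of treatment allocation/randomization through 28 days following cessation of treatment, all adverse events must be reported by the investigator". Note a to the flow chart (6.0) adds that "The post-trial visit will occur approximately 28 days following administration of the study drug"; that visit repeats the examination, ECG, vital signs and laboratory tests.

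On follow-on ART, Section 2.1 rules out a start before Day 10 and says that "the Sponsor recommends that ART initiation occurs on or before Day 14 post-dose", but also that "The initiation of follow-on ART is not a requirement for participation in the study". The regimen is chosen subject by subject. Section 5.5 allows an earlier start to be discussed with the Sponsor where there is a strong indication.

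**The concern.** The protocol encourages every subject to begin another active treatment partway through the safety window. A single 28-day incidence per dose level would then mix events on MK-8583 alone with events on an individually chosen regimen, and would mix subjects who took ART with subjects who did not. At six subjects per panel, one or two events caused by ART would visibly move the incidence.

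Viral load seems to be handled with more care: for subjects who start ART as planned, "the final blood draw for viral load (VL), viral resistance, or PK will occur on the day of ART initiation", and flow-chart note m says that "viral resistance may be collected up to and including the day of ART initiation". Safety data have no counterpart.

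At stake is the condition attached to both formal hypotheses. A dose level meets the primary viral-load criterion or the secondary TFV-DP criterion only if its safety and tolerability are also judged acceptable (8.2.4). If that judgement rested on events attributable to ART, a dose could be marked down wrongly.

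**Working it through.** The plan gives no figure on this point, so there is none to reproduce. The checks are how much of the safety data is exposed, and whether the information needed to read it is collected.

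**Share of the window after ART start**

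Inputs: window 28 days = 672 h (7.2); earliest planned start Day 10 = 240 h (5.5); latest recommended start Day 14 = 336 h (2.1).

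Share = (672 − start) / 672.

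- Day 10: (672 − 240)/672 = 432/672 = 64.3%, or 18 of 28 days.
- Day 14: (672 − 336)/672 = 336/672 = 50.0%, or 14 of 28 days.
- No ART: 0%.

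If time is counted only to a final visit moved by the 72 h window of Table 7, a visit at 25 days gives (25 − 10)/25 = 60% and (25 − 14)/25 = 44%; a visit at 31 days gives 21/31 = 68% and 17/31 = 55%.

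Uptake is not stated. Under assumed uptake, the share of panel person-time is:

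| Assumed uptake | Day 14 start | Day 10 start |
|---|---|---|
| 50% | 25% | 32% |
| 75% | 38% | 48% |
| 100% | 50% | 64% |

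These are shares of time. The documents give no expected timing of events, so they cannot be read as shares of events.

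**Scheduled assessments affected**

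From the flow chart, and for laboratory tests also Section 12.3 (1 pre-trial + 3 in the treatment period, one of them pre-dose, + 1 post-trial):

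- Laboratory tests: 3 post-dose occasions, 1 of them (672 h) after planned ART.
- ECG and vital signs: 4 post-dose occasions, 1 of them after planned ART.

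The last assessment before 672 h is at 168 h, which is 240 − 168 = 72 h before the earliest planned ART start. The bands of Table 7 overlap at 168 h. Even the wider 24 h allowance gives 192 h, still before 240 h.

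**Decisions and analyses exposed**

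- Dose selection between panels needs safety data through at least 168 h (4.2.2, 5.2.1.2): before planned ART.
- The primary viral-load model uses pre-dose and 168 h only (8.2.4): before planned ART. The sample size and power in 8.2.6 concern the same 168 h change and are untouched.
- The 28-day incidence and the 672 h summaries are exposed.

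**Is the information collected?**

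| Needed to read a late event | Where it is recorded |
|---|---|
| Event start and stop dates | Table 8 (7.2.4) |
| ART taken and when | Concomitant medications (7.1.1.5.2) |
| Whether another drug explains it | Physician's causality judgement, required for every event (7.2.4, Table 8) |

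All three are present. In a panel of six, each event with onset after ART can be identified individually.

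**The case for a change.** The strongest case for a change is that recording is not reporting. Section 8.2.4 commits no table to the causality judgement, and that judgement does not reach a laboratory, ECG or vital-sign shift at 672 h that nobody reports as an adverse event. The confounding can also be specific. The protocol names the kidney as a main preclinical target (4.1.2) and links TDF to reduced kidney function (4.1.1). A TDF- or TAF-containing regimen is not excluded, so a creatinine change at 672 h could belong to either drug. This is an open-label trial without a concurrent control, where displays are better chosen in advance, and a listing costs little.

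It stands that no display by ART status is promised and that a 672 h value cannot be read without knowing ART status. But the omission is not peculiar to ART: 8.2.4 promises no table by relatedness, severity or body system either. It leaves safety output to clinical judgement throughout, and that latitude already covers a display by ART status.

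The other supports are weaker.

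- The viral-load rules limit sampling. They are not analysis rules: 8.2.4 summarises viral-load reduction at all time points with no provision for ART.
- Section 5.5 says that "In subsequent panels, the Sponsor will provide the site with written guidance, prior to the start of dosing, as to the time" TFV-DP is expected to fall below 100 nM, so exposure to ART could differ by dose. Assuming TFV-DP proportional to dose and guidance that follows it exactly, 150 mg against 100 mg shifts the time by log2(1.5) = 0.585 half-lives. At the 65-136 h half-life of 4.1.2 that is 38-80 h, or 6-12 points of the 672 h window. That is possible, not shown, and 2.1 states the Day 14 recommendation for all panels alike.
- The acceptability condition has no numerical criterion, and nothing ties it to the 28-day incidence alone.

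**Conclusion.** The observation is accurate, but it concerns a display detail that analysts can settle sensibly from data already collected. It does not call for a change to the plan. For a subject who starts ART on Day 10-14, 50-64% of the adverse-event window follows ART start, along with one of three post-dose laboratory occasions and one of four ECG and vital-sign occasions. No stated number, threshold or decision rule comes out wrong. The full 28-day incidence in all dosed subjects remains a proper summary in its own right, and a pre-ART table would cover only about 10-14 days in a handful of subjects.

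This conclusion assumes that ART starts no earlier than Day 10 (5.5 leaves room for exceptions), that ART start dates are captured with concomitant medications, and that whoever judges the safety profile reads late events against those dates. Uptake is unknown, so the share for a whole panel could lie anywhere from 0% to 64%.

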There will be a break between dosing of panels to allow for review of all available safety, PK, and viral dynamic data to inform dose selection in the following panel. It is estimated that this review will take approximately 30-40 days. Because plasma MK-8583, plasma TFV, and PBMC TFV-DP PK data from healthy subjects are expected to be similar to that of HIV-1 infected subjects, PK data from single doses administered to healthy subjects in Protocol 001 will also be used to aid in the selection of doses for the present study to ensure that plasma MK-8583 levels do not exceed the exposure cap.

The specific dose selected for Panel B will depend on data from Panel A. Assuming PK data indicate that higher exposures maintain safety margins, a higher dose may be tested to see if it delivers greater efficacy. Alternatively, if 100 mg generates exposures in HIV-infected subjects that are higher than what was seen in healthy subjects, or if safety concerns arise, a lower dose may be tested. After Panel B, the Sponsor will assess the utility of testing a third dose in Panel C to further explore PK, PD, and the safety profile of the compound.

Additionally, safety data through at least 168 hours post-dose, including AEs, standard laboratory safety tests, VS, and 12-lead ECGs, physical examinations (PEs) will be reviewed by the Sponsor and the investigator prior to dose escalation, and the decision to proceed to a new dose level will be based upon acceptable safety of MK-8583 at the previous dose. The doses selected for Panels B and C in this study will not exceed the maximum dose of 150 mg previously administered to healthy subjects.

The reduction in VL for each dose level will be compared to historical placebo data from clinical trials previously conducted by the Sponsor. Given the overall favorable safety profile of MK-8583 in preclinical and clinical testing to date, a placebo control to minimize investigator and subject bias with respect to adverse experiences is not deemed necessary.

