Primary Objective (Pharmacodynamics): The log₁₀ plasma HIV-RNA (copies/mL) measurements from subjects in all panels will be pooled and analyzed based on a longitudinal data analysis model containing fixed effects for dose level, time (pre-dose, 168 hrs post-dose) and dose level by time interaction, and a random effect for patient. The change from baseline for each dose level at 168 hours post-baseline will be estimated from this model. A posterior distribution for the true mean change from baseline at 168 hours will be generated for each dose level using flat priors under a normal likelihood assumption. Historical placebo data from recent monotherapy studies in HIV-1 subjects (MK-0518 Protocol 004, MK-1439 Protocol 005, MK-6186 Protocol 007, and MK-1972 Protocol 003) will be separately analyzed based on a longitudinal data analysis model containing fixed effects for study and time (pre-dose, 168 hours post-dose), and a random effect for patient. The change from baseline for placebo at 168 hours post-baseline will be estimated from this model, and a posterior distribution for the true mean change from baseline at 168 hours will be generated using flat priors under a normal likelihood assumption. Using the posterior distributions for each dose level and placebo, the posterior distribution of the true mean difference between each dose level and placebo will be generated, and the posterior probability that the true mean difference in the log₁₀ plasma HIV-1 RNA reduction from baseline between MK-8583 and placebo is at least 0.5 log₁₀ copies/mL will be calculated. An 80% posterior probability for at least one dose level that also exhibits an acceptable safety and tolerability profile will satisfy the primary PD hypothesis.

Power

If the true SD of the log₁₀ reduction from baseline in plasma HIV-RNA at 168 hours post-dose is 0.25(0.4) for MK-8583, there is ~80% power to yield at least 80% posterior probability that the true mean difference in the plasma HIV-1 RNA reduction from baseline

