mean change from baseline at 168 hours will be generated using flat priors under a normal likelihood assumption. Using the posterior distributions for each dose level and placebo, the posterior distribution of the true mean difference between each dose level and placebo will be generated, and the posterior probability that the true mean difference in the log₁₀ plasma HIV-1 RNA reduction from baseline between MK-8583 and placebo is at least 0.5 log₁₀ copies/mL will be calculated. An 80% posterior probability for at least one dose level that also exhibits an acceptable safety and tolerability profile will satisfy the primary PD hypothesis. For each dose level, the posterior probability that the true mean log₁₀ plasma HIV-1 RNA reduction from baseline is at least 0.5 log₁₀ copies/mL will also be calculated. Similar exploratory analyses may be performed using viral load measurements at baseline and specified post-baseline time points.

Secondary (Pharmacokinetics)

Separately for each PK parameter, individual values of TFV-DP in PBMC PK parameters AUC_{0-168hr}, C_{max}, and C_{168hr} from subjects in all panels will be pooled, natural log transformed and analyzed based on a linear model containing a fixed effect for dose level. The 95% confidence intervals for the least squares means by dose level will be constructed on the natural log scale and will reference the t-distribution. Exponentiating the least-squares means and lower and upper limits of these confidence intervals will yield estimates for the population geometric means and confidence intervals about the geometric means on the original scale. The posterior probability that the true GM C_{168hr} PBMC TFV-DP level is $\geq 0.1 \mu\text{M}$ will be calculated for each dose level using flat priors under a normal likelihood assumption. An 80% posterior probability for at least one dose level that also exhibits an acceptable safety and tolerability profile will satisfy the secondary PK hypothesis.

MK-8583 plasma AUC_{0-last}, AUC_{0-inf}, C_{max}, CL/F and V_z/F, and TFV plasma AUC_{0-last}, AUC_{0-inf} and C_{max} will be analyzed in a similar fashion.

Descriptive Statistics

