Individual values will be listed for each PK parameter by dose level, and the following (non-model-based) descriptive statistics will be provided: N (number of subjects with non-missing data), arithmetic mean, standard deviation, arithmetic percent CV (calculated as $100 \times \text{standard deviation}/\text{arithmetic mean}$), median, minimum, maximum, geometric mean, and geometric percent CV (calculated as $100 \times \sqrt{\exp(s^2) - 1}$, where s^2 is the observed variance on the natural log-scale).

The above descriptive statistics, as well as a mean plot will also be provided for VL reduction by dose level and all time points.

Secondary and Exploratory (Pharmacokinetic/Pharmacodynamic)

The PK-PD and dose-PD association of MK-8583 will be explored. Graphs to visualize the association of the reduction in log₁₀ plasma HIV-1 RNA levels with TFV-DP in PBMC by parameters and dose will be generated. Exploratory linear and/or non-linear model fits may be considered, as appropriate. Exposure levels and doses that result in various proportions of the population (e.g., 80%, 90%) that have at least 0.5 log₁₀ reduction from baseline in plasma HIV-1 RNA levels with high confidence may be estimated.

The duration of anti-retroviral suppression after single dose MK-8583 will be evaluated with individual plots across time.

For PBMC levels of TFV-MP, descriptive statistics (similar to those of secondary PK parameters) will be provided by dose.

General

For all analyses, data will be examined for departures from the assumptions of the statistical model(s) as appropriate; e.g., heteroscedasticity, nonnormality of the error terms. Distribution-free methods may be used if a serious departure from the assumptions of the models(s) is observed, or suitable data transformations may be applied.

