8.2.6 Sample Size and Power

If the true SD of the log₁₀ reduction from baseline in plasma HIV-RNA at 168 hours post-dose is 0.25(0.4) for MK-8583, there is ~80% power to yield at least 80% posterior probability that the true mean difference in the plasma HIV-1 RNA reduction from baseline between MK-8583 and placebo is at least 0.5 log₁₀ copies/mL, if the true mean log₁₀ reduction is at least 0.7 log₁₀ (0.8 log₁₀) with N=6 subjects in a Panel. It assumes the historical placebo sample size of 20 with mean reduction of 0 log₁₀ and SD = 0.25. The information of placebo data was from historical placebo data of recent monotherapy studies in HIV-1 subjects (MK-0518 Protocol 004, MK-1439 Protocol 005, MK-6186 Protocol 007, and MK-1972 Protocol 003). The SD of MK-8583 is estimated based on MK-8591 Protocol 003 and MK-8507 Protocol 003 studies (SD ranges from 0.24 to 0.4).

A posterior probability threshold P%=80% is chosen. A favorable posterior probability threshold is defined when the true mean HIV-1 reduction > 0.5 log [relative to Placebo] is >P%; there is relatively low probability of a favorable outcome when the true mean reduction is < 0.5 log₁₀ copies/mL (about 20% or less) and relatively high probability for favorability when the true mean reduction is > 0.7 log₁₀ copies/mL (about 80% or more), assuming a true SD = 25%.

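### Does pooling four historical placebo studies into one common 7-day change undermine the plan's 20% and 80% figures?

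*Combined protocol and SAP*

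**What the plan says.** Section 8.2.4 describes two separate longitudinal models. The MK-8583 model has "fixed effects for dose level, time (pre-dose, 168 hrs post-dose) and dose level by time interaction, and a random effect for patient". The historical placebo model, which covers four named sponsor studies, is a "model containing fixed effects for study and time (pre-dose, 168 hrs post-dose), and a random effect for patient"; Section 8.1 repeats it. Each gives a posterior for the mean 168-hour change under flat priors and a normal likelihood. From these, "the posterior distribution of the true mean difference between each dose level and placebo will be generated", and a dose succeeds if the probability that the difference is at least 0.5 log10 reaches 80%. Section 8.2.4 also reports, for each dose, the probability that the reduction from baseline alone is at least 0.5.

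For planning, Section 8.2.6 says: "It assumes the historical placebo sample size of 20 with mean reduction of 0" log10, and gives a placebo SD of 0.25. With six subjects per panel, it claims roughly 80% power at a true reduction of 0.7 (drug SD 0.25) or 0.8 (drug SD 0.4). It adds that "there is relatively low probability of a favorable outcome when the true mean reduction is" below 0.5, putting that probability at about 20% at most. Section 4.2.3.3 makes the same claim.

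The historical comparison is disclosed in Sections 1.0 and 2.1, and in Section 4.2.2: "The reduction in VL for each dose level will be compared to historical placebo data from clinical trials previously conducted by the Sponsor".

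**The concern.** With two time points, the study term absorbs only differences in viral load level and drops out of the change from baseline. The single time effect is then one change imposed on all four studies. Two components of variation are left out: the effect of between-study differences on the pooled placebo mean, and any gap between that mean and the change untreated subjects in this trial would have shown. If tau is above zero, the posterior for the difference is too narrow and the 80% rule is passed more often than intended at a true difference of 0.5. The historical mean is the only placebo information in the deciding contrast, and the documents give no per-study placebo means, no tau and no argument for exchangeability. The general model check ("data will be examined for departures from the assumptions of the statistical model(s) as appropriate; e.g., heteroscedasticity, nonnormality of the error terms") does not name differences between studies. Its remedies, distribution-free methods or transformations, would not deal with them.

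**Working it through.** **Inputs from Section 8.2.6:** six subjects per panel; drug SD 0.25 or 0.4; 20 placebo subjects with mean reduction 0 and SD 0.25; margin 0.5; threshold 80%, for which z = 0.8416. **Assumptions, not in the documents:** the value of tau, and four equally weighted historical studies.

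**1. Reproduce the plan (tau = 0).** SE = sqrt(SD²/6 + 0.25²/20).
- SD 0.25: sqrt(0.010417 + 0.003125) = 0.1164. Power at 0.7 = Phi(0.2/0.1164 − 0.8416) = 81.0%.
- SD 0.4: sqrt(0.026667 + 0.003125) = 0.1726. Power at 0.8 = Phi(0.3/0.1726 − 0.8416) = 81.5%.
- At a true difference of 0.5, success = Phi(−0.8416) = 20%.

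A version with unknown variances (t-based posterior, simulated) gives power of about 79% and 80%, and success at 0.5 of about 19% and 20%. The stated figures reproduce.

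**2. Planned rule with tau above zero.** The rule still uses SE, but the estimated difference has SD S = sqrt(SE² + 1.25·tau²): tau²/4 for the pooled mean plus tau² for carrying it to a new trial. Success at 0.5 = Phi(−0.8416·SE/S). Power = Phi((effect − 0.8416·SE)/S), where effect is the true reduction minus 0.5.

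| tau | Success at 0.5, SD 0.25 | Power at 0.7 | Success at 0.5, SD 0.4 | Power at 0.8 |
|---|---|---|---|---|
| 0.05 | 22.4% | 78.5% | 21.2% | 80.3% |
| 0.10 | 27.2% | 73.6% | 24.0% | 77.4% |
| 0.20 | 34.9% | 65.7% | 30.4% | 70.8% |

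Success at 0.5 stays within 2 points of 20% up to tau = 0.045 (SD 0.25) or 0.067 (SD 0.4). Power stays at 78% or more up to 0.056 or 0.091.

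**3. Which part comes from the missing study-by-time term?** Replace S by sqrt(SE² + tau²/4), which counts only the pooled mean. Success at 0.5 is then 20.5% and 20.2% at tau 0.05, and 22.0% and 20.9% at tau 0.10 (SD 0.25 and 0.4). At tau 0.10 and SD 0.25, that is about 2 of the 7 excess points. The rest is carry-over to the new trial.

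**4. How far below 0.5 does the excess reach?** Success equals 20% at a true difference of 0.5 − 0.8416·(S − SE). At tau 0.10 this is 0.5 − 0.8416·(0.1614 − 0.1164) = 0.462 (SD 0.25), and 0.5 − 0.8416·(0.2056 − 0.1726) = 0.472 (SD 0.4). Below those values the rate is still under 20%.

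**5. What the alternative would cost.** Take a random study-by-time effect with the predictive placebo change for a new study and a half-normal prior on tau. This was simulated with 20,000 trials, four studies of five subjects (an assumed equal split of 20) and known SDs. If the studies truly agree (tau = 0) and the prior scale is 0.1, power falls from 81.0% to about 76% (SD 0.25) and from 81.5% to about 79% (SD 0.4). Scales of 0.05 and 0.2 give 79% and 72% at SD 0.25. At tau 0.10 with scale 0.1, success at 0.5 is 21.7%, still above 20%. Each study mean has SE 0.25/sqrt(5) = 0.11, as large as the tau of interest, so four studies of this size barely inform tau.

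**The case for a change.** The strongest case for a change is that the gap is real and the first step is nearly free. The model does force one common change. The published error rates do rest on little between-study variation, and no section says so. At tau 0.10 both rates worsen under the planned rule: success at 0.5 rises to 27.2% and power falls to 73.6% (SD 0.25). The placebo-free probability does not decide anything, and it is itself exposed to drift in this trial. The sponsor holds the historical data, so a table by study would cost little. In an open-label trial, a variance term chosen after the viral loads are seen would look data-driven.

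The description of the model and the arithmetic stand. The step from there to a required change does not. The material range depends on a tau of about 0.10 that nothing in the documents supports. If the planning SD of 0.25 is the total SD of the pooled placebo changes (not stated), tau = 0.10 would already be 0.01/0.0625 = 16% of that variance, and 0.20 would be 64%. The rates with tau above zero average over drift in either direction, so they show no bias. A table by study and a sentence of caveat would be reasonable disclosure, but they would not alter which dose passes the rule.

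**Conclusion.** The concern does not call for a change. The placebo model estimates one common 168-hour change and applies it unchanged to this trial, so the quoted figures assume little between-study variation: tau below about 0.05 log10 at drug SD 0.25, or about 0.07 at drug SD 0.4, to keep success at 0.5 within 2 points of 20%. That assumption goes unstated, but no stated figure is shown to be wrong, because the plan claims only approximate values and those reproduce.

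The absent study-by-time term by itself moves success at 0.5 to only 22.0% or 20.9% at an assumed tau of 0.10. The larger part is the price of a historical control, which the protocol chose openly for a small proof-of-concept trial. The contrast with the MK-8583 model is also weaker than it looks: the dose-by-time interaction is what yields a change for each dose, whereas a fixed study-by-time term would give four placebo changes and require a weighting rule.

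The predictive random-effect model is a fair trade-off that the sponsor may decline. It would bring power at SD 0.25 to about 72–79%, depending on the prior scale, even if the studies agree, and the prior would largely set the answer. These conclusions rest on assumed values of tau and four equally weighted studies; the simulated cost also assumes five placebo subjects in each.
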